## **6.2** Study Procedure, Visit Descriptions and Adherence

To ensure consistency of the manualized therapy, each type of visit described below must follow the Treatment Manual. Adherence to the manualized therapy will be reviewed by monitoring of data and or rating videos of these visits as part of the data review process. All criteria for a visit type should be completed as a part of the visit series, which may take place over more than one day.

# 6.2.1 Prescreening, Screening and Baseline Evaluation (Pre-study, Visit 1)

All individuals who are prescreened, as defined in this section, should be assigned a screening number and recorded on the Subject Screening Log where information on the selection of potential subjects in the trial should be collected. Prospective participants will be prescreened by telephone according to an IRB-approved script to learn if they meet basic eligibility criteria.

After telephone screening is completed, each potential participant will be given the informed consent form (ICF). The screening number will be used on all subject records prior to enrollment, including the ICF. After signing the ICF, participants will provide a medical and psychological history through interview and will undergo a general physical examination, performed by a physician who is not the Clinical Investigator. The examination will involve the following procedures: Blood pressure, pulse, height, weight, body temperature, examination of head, eyes, ears, nose, throat, skin, heart, lungs, abdomen and extremities, brief neurological exam (cranial nerves 2-12, sensory, motor, reflexes and cerebellar function), ECG, clinical laboratory assessments to determine study eligibility (see Section 10.0 for list of laboratory tests). Tinnitus and chronic pain symptom severity will be collected using a visual analog scale in subjects with a medical history of these conditions. In addition, Human Immunodeficiency Virus (HIV) and, if indicated, Hepatitis C Virus (HCV) serology will be performed. If there is a confirmed positive HIV serology, it will be kept confidential with the exception of reporting to the South Carolina Department of Health and Environmental Control as required by law, with the Department of Health informing the home state of any individual not residing in South Carolina. Likewise HCV serology will be kept confidential except for reporting to the South Carolina Department of Health and Environmental Control within seven days of discovery as required by law. Appropriate referral for counseling and treatment will be made as necessary. The clinical laboratory values will not be captured in the Case Report Form (CRF), but will be used to establish eligibility and will be kept with the subject's source record. A urine-dip pregnancy test for females of childbearing potential and the drug screen will be performed as well. If, upon examination, there are questions raised about possible medical problems, the investigators will request a review of participant medical records and request additional tests or assessments as indicated. If it is determined that the participant has Hepatitis C or well-controlled hypertension, further evaluation will be performed as described in Section 6.0.

A blinded independent rater who will not be present during any of the therapy sessions will administer the CAPS and assess the participant on the GAF. To establish independent rater reliability, the investigators will have the option to video record the screening CAPS interview in as many instances as necessary. The C-SSRS will also be

administered at screening to assess suicide risk. Suicide risk will also be assessed via psychiatric interview. The Clinical investigator and independent rater will use medical records, communication with the participant's treating psychiatrist or therapist if applicable and psychiatric interview to assess potential risk to others. The participant will complete the BDI-II, PTGI (in reference to time since the trauma), PSQI, DES-II and NEO-PI. The entire visit should take between 1.5 and 2.5 hours. Screening may take place over more than one day and up to four months prior to Visit 1 (enrollment). The participant may also have the first preparatory session (Visit 2) prior to enrollment.

If eligibility is confirmed, the participant will be enrolled and will be issued a subject number and contacted to schedule introductory non-drug psychotherapy sessions and first experimental session. Any participant who must discontinue a medication will, after consultation with the prescribing physician, be given a schedule to begin tapering off that medication so washout will be completed before the first experimental session, with the interval between the start of washout (the last day the medication was taken) and the first experimental session being at least five times the drug and active metabolites' half-life, plus one week for stabilization. The first experimental session will be scheduled to occur after washout is complete, if applicable.

## **6.2.2 Preparatory Sessions (Visits 2-4)**

The investigator will inquire about any possible changes in the participant's health to ensure that the subject continues to meet eligibility criteria and if applicable, will confirm that they have adhered to the schedule for tapering off medications. In subjects who have pre-existing tinnitus or chronic pain, the visual analog scale will be used to collect the severity of symptoms.

The participant will undergo three 90-minute preparatory non-drug psychotherapy sessions with the investigators at their offices. During these sessions the investigators will gather more detailed history, answer any questions the participant may have, and work toward forming a strong therapeutic alliance. The participant and investigators will discuss goals for the MDMA sessions. They will review the procedures and therapeutic approach, following standard procedures and techniques discussed in the sponsor-developed treatment manual. The investigators will prepare the participant for the upcoming experimental sessions and promote an atmosphere of safety in which to confront traumatic experiences and powerful emotions.

Adherence criteria for preparatory sessions should be completed as a part of one of the three sessions. These elements do not have to be accomplished in any specific order or in every preparatory session. Generally, adherence criteria for these sessions include that the therapists will work with the subject to prepare for MDMA-assisted psychotherapy. The therapists and subject will seek to form a strong working relationship with each other, and they will help the subject prepare for upcoming experimental sessions. Preparatory sessions will promote a safe set and setting for confronting trauma-related memories, emotions, and thoughts, which is intended to develop therapeutic alliance.

The first preparatory session (Visit 2) may take place at the time of the screening and before enrollment. All eligible participants must be enrolled prior to the second preparatory session (Visit 3) and in maximum four months after the screening starts.

During the third and last introductory session the investigators will supply the participant with a set of instructions and restrictions for conduct 24 hours prior to receiving MDMA, including restrictions on food and alcohol consumption. Participants must agree to take nothing by mouth except alcohol-free liquids after 12:00 A.M. (midnight) the evening before the MDMA session. Participants must also refrain from the use of any psychoactive drug, with the exception of caffeine or nicotine, within 24 hours of each MDMA session. Participants must not use caffeine or nicotine for 2 hours before and 6 hours after the dose of MDMA.

Unless a participant is still undergoing medication washout, participants will complete the C-SSRS just prior to beginning the second preparatory session. Participants undergoing medication washout will repeat the C-SSRS at a point after washout is complete but before the first experimental session.

The attendant, described below, will remain with the participant during each overnight stay after each MDMA-assisted psychotherapy session. He or she will have a healthcare background and will undergo specific training for the role. If a participant would like another individual present during the MDMA session, a meeting between the investigators and that individual will be scheduled during the introductory session. Such an individual will not replace the night-time attendant. Introductory sessions may be recorded to audio and video, and participants can receive copies of one or more introductory sessions upon request. All SAEs will be recorded from the time the participant is enrolled at Visit 1.

Adverse Events and medications will be collected as described in Sections 8 and 9 of the protocol.

# 6.2.3 MDMA Sessions [Visits 5, 9, and 14 (Visit 14 for full dose group only)]

Subjects in Stage 1 will receive two experimental sessions of MDMA-assisted psychotherapy blinded with respect to dose, scheduled approximately 3-5 weeks apart. Subjects in the open label third experimental session in Stage 1 will receive experimental sessions with the full dose of MDMA.

Each experimental session will last approximately eight hours followed by an overnight stay at the study site. Experimental sessions will be conducted by the male and female cotherapist team. Procedures for MDMA-assisted psychotherapy will remain the same across all sessions, and all procedures except drug dose will be the same for participants assigned to the full, medium and low dose conditions.

Adherence criteria for experimental sessions should be completed as a part of each experimental session. These elements do not have to be accomplished in any specific order. Generally, adherence criteria for these sessions include that the therapists will

create and communicate a setting of safety and support the subject during periods of inner focus. Therapists will use a largely nondirective approach, following the lead of the subject's inner healing intelligence. Therapists will provide encouragement for staying present with difficult experiences. Therapists may occasionally offer gentle guidance or redirection as a choice to encourage collaborative exploration if the subject repeatedly avoids trauma related material. Therapists will inquire about somatic symptoms and if necessary encourage release of tension through movement, in whatever way feels appropriate to the subject. Therapists will use music to support the experience without being intrusive.

On the day of the MDMA session, the participant will arrive approximately one hour prior to the MDMA session. Continuing eligibility will be confirmed, with confirmation of eligibility including a urine drug screening and, if appropriate, a urine pregnancy test. If the subject continues to meet criteria and the participant reports that he/she followed appropriate rules and restrictions, the session will proceed; a positive pregnancy screen is cause for withdrawal from the protocol, a positive drug screen will be reviewed by the investigator and may be cause for delaying drug administration to a later time, rescheduling the session to a later date, or withdrawing the participant from the study. The sponsor and Clinical investigator will follow any pregnancy detected after the occurrence of an experimental session to outcome.

Before MDMA is administered, the therapists and participant will discuss and review the participant's goals, intentions and concerns and some of the commonly experienced effects of MDMA. Participants will complete the SUD just prior to initial dose administration.

At approximately 10:00 A.M., participants will receive the initial dose of MDMA along with a glass of water. The participant will sit or recline on comfortable furnishings, and there will be eyeshades and headphones if the participant wishes to use them. They will listen to a program of music designed to support their experience by initially aiding relaxation and later evoking and supporting deep emotions and the emergence of unconscious material [99, 100]. They may also request periods of music if they wish. The investigators will also encourage periods of time in which the participant remains silent with eyes closed and with attention focused inward in order to allow for the further unfolding of their inner experience, in accordance with the principles of MAPS' treatment manual [101]. Water and electrolyte containing fluids will be available ad lib throughout the session within the limits described in Appendix A. Food will be available during the latter part of the session. The investigators may record the entire session to video and audio. Participants may receive a copy of audio or video recordings of at least one experimental session upon request. The participant will be encouraged to spend much of the time focusing attention on their inner experience without talking, but may speak to the investigators whenever they wish, and will receive guidance and support as needed. After the first hour, if the participant has not spoken spontaneously, the investigators will check in with him/her about the nature of the experience. For the rest of the experience, as appropriate, the investigators will support and encourage the participant in emotional processing and resolution of whatever psychological material is emerging.

Suicidality will be assessed with the C-SSRS twice during each experimental session (approximately one hour before and five to six hours after drug administration).

Blood pressure and pulse will be measured at the outset of the experimental session, once every 15 minutes for the first 4 hours of the MDMA-assisted session and every 30 minutes for another 2 hours. More frequent measures will be taken as described in section 6.1.2 if the established thresholds are exceeded, or if the subject has a diagnosis of hypertension. For subjects without a diagnosis of controlled hypertension, after viewing baseline values at the beginning of the session, the investigators will only view the blood pressure or pulse values in the case of a medical indication in order to improve the effectiveness of condition blinding. More frequent measures will be taken if the participant exhibits symptoms that could be related to hypertension, hypotension tachycardia or bradycarida. In the event of any medical indication, such as signs or symptoms that could be related to either hypertension or hypotension, the investigators have the option to print out the results during the session.

Participant body temperature will be measured via tympanic thermometer every 60-90 minutes. Participants will complete the SUD every 90 minutes, until the session is over, allowing a window of plus/minus 30 minutes to fit into the psychotherapy process where a natural break occurs. If necessary, the investigators can make a greater number of SUD measurements as their clinical judgment dictates. The investigators will record any spontaneously reported reactions during the session. If subjects who have pre-existing tinnitus or chronic pain mention any changes, the visual analog scale will be used to collect the changes in symptoms.

A supplemental dose half the size of the initial dose may be administered 1.5 to 2.5 hours after the initial dose upon mutual agreement between the investigators and the participant.

Approximately six hours after drug administration, the investigators will administer the C-SSRS.

If there is a support-individual who has previously been asked and has agreed to be present during part or all of the MDMA session, that person may arrive during the session at whatever time has been agreed upon, but will wait in the waiting room until brought back to the session room by one of the therapists.

The investigators will remain with the participant until the physical and psychological effects of the session have substantially subsided and the subject is judged to be in a stable condition and appears to have returned to baseline mental status. The investigators will end recording to audio and video when they have established that the participant has returned to baseline function or is very close to doing so. Both of the investigators conducting psychotherapy reside near the study site and one or both can quickly return to the site if necessary. Throughout the study, at least one of the investigators, or a physician who is covering for them if they are not available, will remain available to participants via 24-hour cellular telephone.

The participant will complete the SOCQ after the end of the experimental session and prior to leaving the treatment facility the next day.

The participant will remain at the study site overnight, in a comfortably furnished suite that allows for accompaniment by a significant other, and the attendant. The attendant will remain in the building during the overnight stay, even if a significant other is present. The attendant will attend to the subject's needs such as food and fluids during the overnight stay. The attendant will be an individual with previous training or experience in supporting individuals in psychological distress. The attendant may be anyone with some training or background in health care, particularly in psychiatric care. If there is an emergency or the participant needs additional support, the attendant can contact the investigators. The participant and if applicable, his or her significant other, will also receive contact information for the investigators during the overnight stay in the case of an emergency or request for additional support. Participants will be encouraged to use much of the time during their overnight stay for rest and for a period of reflection and integration in a quiet atmosphere.

Participants will be instructed not to use caffeine or nicotine for 6 hours after the dose of MDMA. Spontaneously reported reactions, Adverse Events and Medications will be collected as described in Section 8 and 9 of the protocol.

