#### **6.1.2 Safety Measures**

Safety measures will be applied as described below to minimize risks associated with drug-assisted psychotherapy sessions.

Participants will rate their current degree of subjective distress with a single-item, self-report scale, the SUD scale, repeatedly during the MDMA session, with the degree of distress marked along seven points. Subjective psychological distress will be measured periodically throughout each experimental session.

Cardiovascular effects will be assessed via blood pressure and pulse measurement. Blood pressure, heart rate (as pulse) and temperature will be measured periodically during each experimental session. Blood pressure and pulse will be measured at the outset of the experimental session, once every 15 minutes for the first four hours of the MDMA-assisted session and every 30 minutes for another two hours. Participants with controlled hypertension will have blood pressure and pulse assessed every 15 minutes for the first five hours and every thirty minutes for the next three hours. More frequent measurements will be taken as per the judgment of the Clinical Investigator. Blood pressure and pulse will be assessed via an automatically inflating cuff. Body temperature will be assessed via tympanic thermometer every 60-90 minutes. For subjects with a diagnosis of pre-existing controlled hypertension, the results of blood pressure and pulse measurements will be viewed by the investigators as the measurements occur. For subjects without a diagnosis of controlled hypertension, after viewing baseline values at the beginning of the session, the investigators will only view the blood pressure or pulse values in the case of a medical indication in order to improve the effectiveness of condition blinding. The night attendant will print out the blood pressure and pulse results after the session, make a back-up copy, and will seal both copies together in an envelope and write their initials over the seal. This envelope will be part of the source record and will be kept sealed until after unblinding occurs for that subject. In the event of any medical indication, such as signs or symptoms that could be related to either hypertension or hypotension, the investigators have the option to print out the results during the session.

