# 6.2.10 Open-Label Study Segment for Low Dose and Medium Dosage Participants ("Stage 2")

Participants assigned to receive low dose or medium dose MDMA during Stage 1 will undergo three open-label MDMA-assisted psychotherapy sessions that follow a course and schedule similar to Stage 1 for the full dose group except that participants will

undergo one instead of three introductory sessions. After confirming consent and eligibility criteria, participants continuing to Stage 2 will meet with both investigators conducting psychotherapy for a single review and preparatory psychotherapy session before the first open-label MDMA-assisted psychotherapy session. If more than 8 weeks have passed since the primary endpoint, all measures will be repeated for a new baseline prior to the first open-label experimental session. Experimental sessions will be conducted according to procedures described in Section 6.2.3. During the first experimental session, subjects will receive a 100 mg initial dose of MDMA and may receive a 50mg optional supplemental dose of MDMA. At the beginning of each of the second and third experimental sessions, the co-therapists, in consultation with the subject, will decide whether to administer an initial dose of 100 mg or 125 mg initial dose of MDMA. If a 100mg initial dose of MDMA is selected, an optional supplemental dose of 50mg MDMA may be administered. If a 125mg initial dose of MDMA is selected, an optional supplemental dose of 62.5mg MDMA may be administered. If the PI decides not to administer the optional supplemental dose and/or the optional clinical titration dose in a given experimental session, the unused capsules will be kept in their respective inner envelopes inside of the primary container in the safe.

Integrative sessions will be conducted according to procedures described in Sections 6.2.4 and 6.2.6. Phone calls will be conducted according to procedures described in Section 6.2.5.At the secondary endpoint based on procedures described in Section 6.2.7, the Independent Rater will administer the CAPS and GAF. Subjects will complete the BDI-II, PSQI, PTGI (in reference to the start of the study), and DES-II.Administration of the CAPS may be recorded to video.

Investigators will follow the most recent treatment manual in all matters relating to the Open-Label Stage 2 experimental psychotherapy sessions

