#### 7.4.1 Cardiovascular Effects

The full dose of 125 mg, followed by a supplemental dose of 62.5 mg after 1.5 to 2.5 hours, is expected to produce significant but transient, self-limited increases in blood pressure and heart rate. Participants enrolled in controlled trials with MDMA (approximately 5% per trial) have had elevations in blood pressure of above 140/90 mmHg or higher, but none of these individuals needed clinical intervention and blood pressure returned to normal as drug effects waned [68, 75]. Table 2 shows the degree of increase in vital-sign measurements in the investigators' recently completed clinical trial. No subjects in other clinical trials using MDMA have required any clinical interventions for elevated blood pressure, pulse or temperature, and all values returned to normal spontaneously.

The degree of additional blood pressure and pulse elevation after a second dose of MDMA that is half the original dose and given 1.5 to 2.5 hours after the first dose is minimal. Preliminary data gathered by [name], the Clinical Investigator who recently conducted a study of MDMA-assisted psychotherapy in 21 participants PTSD, demonstrates that elevation in blood pressure and heart rate after the supplemental dose does not exceed elevations seen after the initial dose.

Table 2. Physiologic Data: Mean Increases in Vitals over Baseline and Range of Values per Experimental Session

	MDMA	Placebo
	Mean increase (St. Dev.)	Mean increase (St. Dev.)
	[Range of values]	[Range of values]
Systolic blood		
pressure, mmHg	28.21 (14.11)	13.38 (10.40)
	[96-179]	[83-157]
Diastolic blood		
proggura mmUa	15.38 (6.85)	10.94 (6.93)
pressure, mmHg	[56-113]	[60-102]
Heart rate,		
beats/minute	28.13 (11.87)	16.69 (12.35)
	[60-141]	[68-107]
Temperature, °C	0.72 (0.52)	0.42 (0.32)
	[36.6-37.83]	[36.39-37.76]

Group comparisons of vital signs were tested for change pre-session (15 minutes prior) to highest recorded and pre-session to post-session (6 hours post) using t-tests. There was a significantly greater increase in all physiologic measures from pre-session to highest recorded value during experimental sessions for the MDMA group than for the placebo group (p < .05). There were no significant differences when comparing changes from pre-session to post session (p > .05). All values returned to pre-session norms by six hours after session completion.

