# Angina or Myocardial infarction

If a participant experiences ischemic type chest pain, whether or not it is associated with hypertensive crisis, he or she will receive oxygen and an IV and will be monitored as described above. He or she will be given 162 mg of chewable aspirin once nitroglycerin 0.4 mg SL q 5 minutes PRN chest pain pending transport to the hospital. If further evaluation at the hospital reveals that the participant has had an acute myocardial infarction (AMI), he or she will be well within the time frame required for definitive

therapy. The American College of Cardiology/American Heart Association guidelines for the treatment of AMI recommend percutaneous transluminal coronary angioplasty (PTCA) as the treatment of choice when it can be performed within 90 minutes of arrival at the hospital in individuals who present within 12 hours of an episode of chest pain lasting more than 30 minutes and who have ECG evidence of AMI [170].

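### The blood-pressure and pulse threshold rule for MDMA sessions has no stated limit and, for asymptomatic subjects without controlled hypertension, no described way to act

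*Protocol*

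**What the plan says.** - **Threshold rule (protocol 6.2.3).** "More frequent measures will be taken as described in section 6.1.2 if the established thresholds are exceeded". The same sentence gives a hypertension diagnosis as a second trigger. A separate sentence covers symptoms.
- **Viewing (6.1.2, repeated in 6.2.3).** Subjects with controlled hypertension have their values watched live. For all others, once baseline has been seen, "the investigators will only view the blood pressure or pulse values in the case of a medical indication". The stated reason is to protect the blind. Signs or symptoms are given as an example of such an indication.
- **Handling of readings (6.1.2).** An automatic cuff takes the readings. The night attendant prints them after the session and places them in an envelope that is "kept sealed until after unblinding occurs for that subject".
- **Reach.** Section 6.2.3 includes open-label Visit 14 in its heading and adds: "Procedures for MDMA-assisted psychotherapy will remain the same across all sessions". For open-label Stage 2, section 6.2.10 says: "Experimental sessions will be conducted according to procedures described in Section 6.2.3".
- **Appendix A.** For ischemic chest pain, and in the same terms for stroke, "he or she will receive oxygen and an IV and will be monitored as described above". Both entries mention hypertensive crisis.
- **SAP 8.9.4, Vital signs.** Readings above a cutoff fixed in advance are to be tabulated. No value is given.

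**The concern.** The protocol promises a safeguard that responds to a number, but the supplied text contains no number and gives nobody the task of noticing when it is passed. Symptoms have their own sentence in 6.2.3, so the threshold clause should add protection for a subject who feels well. That is the case in which, without controlled hypertension, nobody is assigned to look.

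Two decisions could be made without the information. One is whether to give the supplemental dose 1.5 to 2.5 hours after the first. The other is whether to proceed to session 2 while the session 1 readings are still sealed. In open-label sessions the investigators remain restricted from viewing, although the dose is known to everyone.

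The contrast within Appendix A is plain. Temperature has actions at rises of 1 °C and 1.5 °C, and serum sodium has a limit of 125 mEq/L. Blood pressure and pulse have none.

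**Working it through.** The plan gives no figure to reproduce. The check is a search of the text followed by a count.

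**1. Is there a limit?**
- Section 6.1.2 gives a denser schedule for controlled hypertension and otherwise leaves extra measurements to the Clinical Investigator's judgment. It has no limit, whether the pointer in 6.2.3 is read as referring to the extra measures or to the thresholds.
- The value 140/90 occurs twice: as an eligibility criterion (5.3.2) and in a description of earlier trials (7.4.1). Neither is an in-session trigger.
- SAP 8.9.4 names a cutoff for tabulation only, without a value.

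**2. Who would see an exceedance?** Schedule from 6.1.2 and 6.2.3 for a subject without controlled hypertension:
- 1 at outset + 4 h × 4 per hour + 2 h × 2 per hour = 1 + 16 + 4 = 21 readings.
- Readings after baseline: 21 − 1 = 20, with no assigned in-session viewer unless a medical indication arises.
- Two blinded sessions: 40 of 42.
- With controlled hypertension: 1 + 5 × 4 + 3 × 2 = 27 readings, all viewed live. For these subjects only the value of the limit is missing.

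**3. Which decisions does this touch?**
- Supplemental dose, assuming the 15-minute clock starts at the initial dose: 1.5 h × 4 = 6 to 2.5 h × 4 = 10 readings come before the decision.
- Session 2 (Visit 9) is 3 to 5 weeks after session 1 (Visit 5). Unblinding is at Visit 13, one month later (4.35 weeks). Session 1 readings therefore stay sealed for 3 + 4.35 = 7.35 to 5 + 4.35 = 9.35 weeks, which spans session 2.

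**4. How far does the viewing restriction reach?** It depends on hypertension status, not on whether the session is blinded. For 24 completers:
- Blinded: 24 × 2 = 48 sessions.
- Open-label: 12 × 1 at Visit 14, plus up to 12 × 3 = 36 in Stage 2, so up to 48.
- Upper end: 48 of 48 + 48 = 96. If nobody enters Stage 2: 12 of 48 + 12 = 60.

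These are upper limits for the restriction, because the number of subjects with controlled hypertension is not known.

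**5. What does Appendix A point back to?** The general part of Appendix A gives the attending team and a cardiac-arrest response. Section 7.5 lists equipment and emergency drugs. No earlier text says what counts as a hypertensive crisis or which of these is the monitoring meant.

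**The case against.** **Limits may exist elsewhere.** Section 7.5 reuses contingency plans from the earlier trial, and both 6.2.3 and SAP 8.9.4 speak of limits as already fixed. This stands. A reader might infer that no limits were ever set, but the documents show only that the supplied text does not state them. The cross-reference still needs repair, because 6.2.3 points to 6.1.2 and not to those plans.

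**A medical indication is not confined to symptoms, and the Clinical Investigator may order more measurements.** Both are true, and an exceedance would naturally count as an indication. But someone must first learn of it. The cuff may be able to alarm; the text does not say so or link an alarm to the rule.

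**Restricted viewing is a deliberate price for the blind.** This stands for the blinded sessions, and the restriction should stay there. In open-label sessions the stated purpose has lapsed. A reader might infer that open-label readings also stay sealed. They need not, because sealing ends at unblinding, which comes before Visit 14 and Stage 2. Only the viewing restriction carries over.

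**Appendix A has cardiovascular content.** A reader might infer that it has no cardiovascular procedure at all. That is wrong: the cardiac-arrest response is there, and section 7.5 supplies a crash cart with antihypertensives. What is missing is a definition and a clear reference.

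**The risk looks small.** Section 7.4.1 reports that "elevation in blood pressure and heart rate after the supplemental dose does not exceed elevations seen after the initial dose", and of the earlier trial that "All values returned to pre-session norms by six hours after session completion". It also reports that other MDMA trials needed no intervention for vital signs. Vascular disease and uncontrolled hypertension are excluded, and an ACLS-certified physician attends. This stands and limits the severity. The documents give no support for inferring that an asymptomatic exceedance has caused harm.

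**Conclusion.** The concern holds as a moderate defect that should be corrected. Followed exactly, the plan leaves a stated safety rule unable to act on an asymptomatic exceedance in subjects without controlled hypertension. In those subjects, 20 of 21 readings per session have no assigned in-session viewer. The viewing restriction also covers between 12 of 60 and 48 of 96 planned sessions in which its reason no longer applies, probably through oversight.

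These counts assume 24 completers, the routine schedule, no medical indication and no controlled hypertension. The finding on the limit is confined to the supplied protocol and SAP.

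The practical effect depends on where the limits lie. The earlier trial excluded controlled hypertension, so it is the closest comparison. Its separate maxima in MDMA sessions were 179 mmHg systolic, 113 mmHg diastolic and 141 beats/min (section 7.4.1), so limits above those values would not have been reached there.

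**What to change.** 1. State systolic, diastolic and pulse limits in 6.1.2, at a clinical action level chosen by the sponsor's medical team. Use the same values for the SAP 8.9.4 cutoff, or explain the difference.
2. Set the automatic cuff to alert only on exceedance, if the device supports it; the documents do not say. State that an exceedance is a medical indication that permits viewing and more frequent measures, and that it is considered before the supplemental dose and before session 2.
3. Limit the viewing restriction to blinded Visits 5 and 9. Sealing needs no change.
4. In Appendix A, define hypertensive crisis and name the monitoring that the back-reference means.

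The cost is a protocol amendment, a matching SAP entry and possibly a device setting, with no extra visits. The third change is free. The downside is that an alert may hint at the dose in the few blinded sessions where it fires. Log each one beside the belief-of-assignment rating collected the next day (section 6.1.3), so that its effect on the blind can be reported.
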